The Fine Motor Scale provides a measure of visual-motor ability: It reflects the output side of visual organization. The tasks require visually directed motor planning and involve visual discrimination and motor control.

The Receptive Language Scale measures the child's ability to process linguistic input. The abilities covered in this Scale are auditory comprehension and auditory memory.

The Expressive Language Scale provides a measure of the child's ability to use language productively. The primary areas covered in this Scale are speaking ability and language formation. These tasks also involve auditory comprehension and auditory memory.

MSEL Reliability and Validity

The MSEL has demonstrated positive results with test-retest and inter-rater reliability. In addition, the MSEL is strongly correlated with multiple assessment tools used to assess cognitive ability in the infant population.

Reliability: According to Mullen, the median internal consistency split-half coefficients (Guilford's formula) for the five Mullen scales range from .75 to .83 and for the composite, .91. (2) Test-retest reliability (with a 1- to 2-week interval between tests): for the Gross Motor Scale of the original Mullen scales, the correlation between tests was .96, and the median correlations on the "cognitive" scale were .84 (with a range of .82 to .85) for children ages 1 to 24 months and .76 (with a range of .71 to .79) for children ages 25 to 56 months. (3) Inter-rater reliability: correlations among raters ranged from .91 to .99 for age groups between 1 and 44 months.⁶⁴

Validity: According to Mullen, concurrent validity testing showed the Mullen scales to have stronger correlations with instruments that measured similar skills than those measuring different skills. The correlations of the Mullen "cognitive" scales with the Bayley Mental Development Index (MDI) were higher (.53 to .59) than their correlations with the Bayley Psychomotor Development Index (PDI; .21 to .52). The ELC also was more strongly correlated with the MDI (.70) than with the PDI (.43). Conversely, the Mullen Gross Motor scale was more strongly correlated with the Bayley PDI (.76) than

with the MDI (.30). Similarly, the Mullen Receptive Language scale had a higher correlation with the Preschool Language Assessment Auditory Comprehension (.85) than with Verbal Ability (.72), while the converse was true with the Mullen Expressive Language Scale (.72 for auditory and .80 for verbal). Finally, the Mullen Fine Motor scale was strongly correlated with the Peabody Fine Motor Scale, across four age groups of children between the ages of 6 and 36 months (correlations ranged from .65 to .82). (2) Predictive validity: no information available.⁶⁴

Brain MRI axonal pathway

The identification of the comparison sample will enable us to provide descriptive comparisons of brain MRI axonal pathway myelination between with infants in our primary study sample against those with less severe or no DP.

Using the Cranial Index and Cranial Symmetry Measures, a comparison sample of infants (gender, age and race/ethnicity) with less severe or no DP will be identified by our neuroradiology team members through retrospective chart review from within BCH medical records. Data collection will be limited to Brain MRI and infant characteristics' data that already exists in the medical records. Data including brain MRIs and infant characteristics will be de-identified for storage. Members of the study team will maintain an electronic record of corresponding MRNs in the study log in the event that data verification or additional analyses are needed.

Axonal pathways for infants with DP primary study sample undergoing helmet therapy and those of the comparison sample will be constructed then examined for differences axonal pathways.

Data Management

Data will be managed and stored by the Cardiology Clinical & Research Regulatory Group at BCH. Baseline cranial index and cranial symmetry measurements (obtained manually and by laser scan) for each of the study subjects will be examined by one the investigators (Neurosurgeon or Plastic Surgeon) to confirm correction. Then one of the other investigators (a neuroradiologist with experience in performing FDNIRS/DCS and Brain MRIs) will examine each of the study subjects independently for changes in brain volume/structure, myelination of axonal pathways, perfusion of cerebral structures and cerebral oxygen consumption for changes pre and post correction. FDNIRS/DCS, brain MRI and MSEL data will be stored into a password protected, secure computer.

Data Analysis

The measures will be quantified according to their respective units of measure and the investigators will prepare a report of the pre and post exam (by FDNIRS/DCS, MRI, and MSEL) findings. The report will include case presentations for each of the study subjects and a description of their comparisons, as specified in the aims. A collective presentation of the findings will be prepared using descriptive statistics (mean, median, mode, and frequencies). Tables and bar graphs will also be used to display the results. Also if the data permits, non-parametric tests (signed-rank) will be used to determine if differences are statistically different from zero when examining the paired observations.

References

1. American Academy of Pediatrics. Positioning and sudden infant death syndrome (SIDS): Update. *Pediatrics*. 1996;98(6):1216-1218.
2. Lennartsson F. Developing guidelines for child health care nurses to prevent nonsynostotic plagiocephaly: Searching for the evidence. *Journal of Pediatric Nursing*. 2011;26:348-358.
4. Task Force on Sudden Infant Death Syndrome. The changing concept of sudden infant death syndrome: Diagnostic coding shifts, controversies regarding the sleeping environment, and new variables to consider in reducing risk. *Pediatrics*. 2005-3006;116(5):1245-1255.
7. Hutchison B, L. Characteristics, head shape measurements and developmental delay in 287 consecutive infants attending a plagiocephaly clinic. *ACTA Paediatrica*. 2009;98:1494-1499.
10. Alley TR. Head shape and the perception of cuteness. *Developmental Psychology*. 1981;17(5):650-654.

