In newborns and infants, MRI is routinely used in the diagnosis and monitoring of conditions such as hypoxic-ischemic injury, brain occupying lesions or neoplasms, stroke, encephalopathy, and white matter injury in preterm infants.³⁶⁻⁴⁷ The typical MRI scan in neonates and infants takes approximately 30-45 minutes. In preparation for the MRI study infants are generally fed, wrapped snuggly, then earmuffs are placed over

their ears to protect them from the tapping sound of the scanner. Some infants also require light sedation to ensure they remain still during the imaging procedure.³⁶

The 3 T field strength is reported to be optimal for MRI's of the neonatal and infant brain. A typical MRI sequence may include a volumetric T1-weighted sequence, T2- weighted axial sequence, a susceptibility-weighted image or an axial diffusion sequence with a calculated apparent diffusion coefficient map, and at least 1-2 MR spectroscopy (MRS) samples.³⁶ Also MRA and MRV may be obtained to look at both the arterial and venous structures respectively.

MRI has been used extensively to diagnose and predict outcomes for infants with hypoxic ischemic encephalopathy and white matter injury of preterm infants. In hypoxic ischemic encephalopathy an array of changes to the brain are observed with MRI and vary according to the timing of the exam. In simple terms, beginning 2-3 days following the injury, T1-weighted images provide information on signal abnormalities or change in the thalamus, putamen, globus pallidi and cortex, while T2-weighted images demonstrate changes to the thalamus and basal ganglia after 7 days. In contrast, diffusion weight images are beneficial in examining the neonatal brain for hypoxic injury in the first few days following the injury and will typically show reduced diffusion in the ventrolateral thalami. MRS is often added to measure lactate, a by-product of tissue injury. In preterm infants MRI is most frequently used to look for white matter injury associated with intraventricular hemorrhage. In this condition high signal intensities are observed on T1-weighted images and hypointense signals are noted on T2 weighted images in the posterior ventricular white matter and frontal white matter.³⁶ Many studies have linked MRI findings of thalamic and white matter injuries to severe cognitive and motor disabilities supporting the use of MRI for the routine examination of infants with suspected brain injury.^{36, 39, 40, 48}

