Some researchers and healthcare providers are concerned that DP may be more problematic than once thought. Concurrently, technological advances now allow researchers to detect diminutive changes in brain structure. In this multidisciplinary descriptive pilot study we will use brain MRI and a cerebral tissue oxygenation monitor to describe if a difference in brain structure and characteristics exist in infants with significant DP before and after correction of the abnormality. Knowledge generated from this study will enable investigators to seek preliminary evidence that brain development is influenced by the shape of the cranial vault, and that changes in brain structure and characteristics occur with helmet therapy. Additionally this study will help to determine the need for a larger investigation of this phenomenon that would further establish an association between DP and developmental delay.

Specific Aims

1. Specific Aim: To describe if differences in brain volume/structure exist by Brain MRI in a sample of infants prior to and following treatment of significant DP with helmet therapy.
2. Specific Aim: To describe if differences in myelination of axonal pathways exist by Brain MRI in a sample of infants prior to and following treatment of significant DP with helmet therapy.
3. Specific Aim: To describe if differences in myelination of axonal pathways exist by Brain MRI in a sample of infants with significant DP compared to infants with similar characteristics but less severe or no DP.
4. Specific Aim: To describe if differences in perfusion of cerebral structures exist by brain MRI in a sample of infants prior to and following treatment of significant DP with helmet therapy.
5. Specific Aim: To describe if differences in cerebral oxygen consumption by Frequency Domain Near Infrared and Diffuse Correlation Spectroscopy (FDNIRS/DCS) exist in a sample of infants prior to and following correction of significant positional head shape deformity
6. Specific Aim: To describe the cognitive ability in five areas of neurobehavioral development in a sample of infants with DP prior to and following helmet treatment using the Mullen Early Scales of Learning (MSEL).

Research Design and Methods

Design: This is a descriptive pilot study.

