Setting: Infant participants meeting inclusion and exclusion criteria will be enrolled through the outpatient plagiocephaly clinics (Neurosurgery and Plastic Surgery clinics) at Boston Children's Hospital, Boston Children's Hospital Waltham and Boston Children's Physicians South (Weymouth)

Table 1.

Inclusion Criteria	Exclusion Criteria

- DP requiring helmet therapy-Term gestation at birth (37 weeks or greater)-Less than/or equal to 8 months of age-No history of major health problem such as birth injury, genetic disorder, intracranial hemorrhage, hydrocephalus, neurologic abnormality-No history of implantable metal device or internal/external orthotic device	
- DP not requiring helmet therapy-Premature gestation at birth (less than 37 weeks gestation).-Greater than 8 months of age-History of major health problem such as birth injury genetic disorder, intracranial hemorrhage, hydrocephalus, neurologic abnormality-History of implantable metal device or internal/external orthotic device-Infants not completing prescribed treatment for correction with a helmet

Primary Study Sample: We believe that a sample size of 10 subjects meeting the inclusion and exclusion criteria in Table 1., will provide enough information to determine the need for a larger investigation of this phenomenon. To ensure the desired sample size of 10 subjects, a convenience sample of 10-15 infants (that includes 5 additional patients for attrition) with DP, recommended for treatment with helmet therapy, will be recruited into this study.

Comparison Sample: In Aim 2 we will retrospectively identify a sample of infants with similar characteristics (gender, age and race/ethnicity), with a less severe form of DP, or no DP to serve as comparisons.

Staff Education: All research staff will be Citiprogram trained. Also, research staff involved in recruiting, consenting and data collection procedures will receive training by the study PI.

Human Subjects: Prior to initiation of study procedures IRB approval will be obtained. The risk of a serious adverse event is unlikely in this study; however there are other inconveniences and risk to participation to be considered as follows:

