If parents do not want to enroll at the time of their clinic visit but are still interested in possibly participating, the consent team will provide them with a copy of the consent form for them to take home and review, along with the study team member's contact information if the family would like to contact them to enroll or ask questions. In these instances where the family would like some time to make a decision, the consent team will ask the parents if they would be willing to have the team contact them by phone a few days after the clinic visit to check in and learn of their decision to participate. The study team will attempt to contact a family to learn of their decision a maximum of 3 times after the in-person clinic visit. If the team is unable to get in touch with the family after 3 attempts, they will stop trying to contact the family. If parents do not want to be contacted and indicate this to the team, there will be no more contact attempts.

Study Procedures: The treatment of significant cranial asymmetry, with cranial remolding orthosis typically commences as early as possible, usually around 3-6 months of age. Treatment involves a lightweight, plastic and foam orthosis made from a 3-D scan of the infant's head. The plastic and foam orthosis (known as a Helmet therapy) is made of a plastic flexible shell lined with polyethylene foam. The orthosis is modified over time to allow for growth and provide a pathway for the infant's head to grow into a more symmetrical shape.

As part of their routine helmet therapy treatment for DP, study participants will be sent to the NOPCO brace center at BCH or CH Waltham for head shape measures including a laser scan of their head. Participants will also have cerebral tissue oxygenation monitoring completed (FDNIRS/DCS) while waiting for the head shape measures to be obtained or following the measures. If recruited at CH Waltham or Weymouth, parents may be asked to go to BCH for the cerebral tissue oxygenation monitoring at a later

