date. Next, arrangements will be made for the study subjects to go to CH Waltham at later date (at a time convenient to the parents and during normal business hours) for MSEL assessment and non-sedated brain MRI. Parents of study subjects will receive instructions on preparation for their day of testing and what they are to expect when they arrive. Parents will be informed that a study team member will be available on the day of the testing and will remain with them throughout the brain MRI. After all initial measures (head shape measures, laser scan, FDNIRS/DCS, MSEL, and Brain MRI) are obtained the study subjects will begin treatment with their helmets. During this time, study subjects will receive routine care and management for correction of the DP, including routine visits with the Neurosurgery or Plastic Surgery clinic physicians, and routine readjustments of their helmets. Upon completion of treatment and resolution of the DP study subjects will have their head shape measures obtained, including a laser scan of their head, cerebral tissue oxygenation monitoring, MSEL and a non-sedated brain MRI. Once again these visits will occur during normal business hours, at a time convenient to the parents. If the subject's routine care and helmet readjustments are taking place at CH Waltham or Weymouth, the subject and their parents may be asked to go to BCH for cerebral tissue oxygenation monitoring. At the end of the second MRI appointment, parents will be offered a CD of their infant's MRI images. These images are not meant for diagnostic purposes and should not be used to inform future treatment decisions for the infant. In the event that the study team is unable to complete the required cerebral oxygen monitoring measures or developmental assessment due to time limitations, parents will be given the option of scheduling additional appointments to complete these measures. There will be no obligation to attend these appointments.

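### Aim 3's comparators come from existing hospital MRIs, but Table 1's term-birth and health-history criteria are never applied to them

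*Combined protocol and SAP*

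**What the plan says.** Under Specific Aims, Aim 3 describes axonal myelination in infants with significant DP "compared to infants with similar characteristics but less severe or no DP". The Comparison Sample paragraph under Research Design and Methods says the team will "retrospectively identify a sample of infants with similar characteristics (gender, age and race/ethnicity), with a less severe form of DP, or no DP". The later Comparison sample paragraph, in the study procedures, says that the neuroradiology team finds these infants by retrospective review of hospital charts and grades their DP by cranial index and cranial symmetry. The section Brain MRI axonal pathway repeats the three matching factors and the head-shape measures. It also limits comparator data to MRIs and characteristics already in the medical record.

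Table 1 requires birth at 37 weeks or later and no "history of major health problem such as birth injury, genetic disorder, intracranial hemorrhage, hydrocephalus, neurologic abnormality". The Primary Study Sample paragraph is where the table is put to use: "a sample size of 10 subjects meeting the inclusion and exclusion criteria in Table 1". Enrollment under these criteria is through the plagiocephaly clinics.

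On why infants have brain MRI, the Technological Advances section says: "In newborns and infants, MRI is routinely used in the diagnosis and monitoring of conditions such as hypoxic-ischemic injury, brain occupying lesions". It adds: "In preterm infants MRI is most frequently used to look for white matter injury associated with intraventricular hemorrhage".

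**The concern.** The cases are term-born infants without major illness. The comparators are infants who happened to have a brain MRI on file and who resemble the cases in gender, age and race/ethnicity. Nothing in the selection rule keeps out an infant scanned because of preterm birth, hypoxic injury or another neurologic condition.

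The outcome makes this important. Aim 3 concerns the internal capsule, optic radiations and arcuate fasciculus, measured by fractional anisotropy and mean diffusivity, and the background describes white-matter injury in preterm infants. If such infants enter the comparison group, health and gestational age differ between the groups along with DP, and the contrast cannot separate them.

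Aim 3 is the only between-group comparison; the other five aims are pre/post within the same infants and are unaffected. The comparison is descriptive, but the pilot is meant to inform whether a larger study is needed, so a misleading contrast could misinform that decision.

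**Working it through.** No figure in the plan is at issue, so the check is mainly a comparison of passages.

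**1. What each place requires of comparators**

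| Place in the protocol | Requirement for comparators | Term birth | Health history |
|---|---|---|---|
| Specific Aims, Aim 3 | similar characteristics; milder or no DP | not stated | not stated |
| Comparison Sample (Research Design and Methods) | gender, age, race/ethnicity; milder or no DP | not stated | not stated |
| Comparison sample (study procedures) | similar characteristics; DP graded by head-shape measures; hospital charts | not stated | not stated |
| Brain MRI axonal pathway | gender, age, race/ethnicity; head-shape measures; existing MRI | not stated | not stated |

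**2. Whether Table 1 could apply by default.** It is tied to the primary sample. It could not carry over whole in any case, because it requires DP needing a helmet and excludes DP that does not. The comparators are by definition infants with milder or no DP.

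**3. Whether the source makes the gap matter.** Comparator scans are existing records. The protocol's own account of routine infant MRI lists brain injury and preterm white-matter injury among its uses. The Incidence section names prematurity and neurological deficits as risk factors for DP, so these factors may relate to head shape as well as to the outcome. Technological Advances also cites an MRI study reporting differences in skull shape and brain tissue between term and preterm infants.

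**4. Which case scan sets the matching age.** Matching is on age, but the reference scan is not named. Each case has two scans, separated by a treatment that averages 4-6 months (note to Table 2). The second comes later: "Upon completion of treatment and resolution of the DP study subjects will have their head shape measures obtained". Since Aim 3 concerns infants with significant DP, the pre-helmet scan is the natural reading. The axonal pathway section says only that the primary sample is undergoing helmet therapy.

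**5. Illustration of size.** The 10 cases are from the protocol. The 10 comparators, the number affected, the tract difference and a common SD are assumptions.

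Shift in comparator mean = (affected / 10) x difference in SD units:
- 1 affected: 1/10 x 0.5 = 0.05 SD; 1/10 x 1.0 = 0.10 SD
- 5 affected: 5/10 x 0.5 = 0.25 SD; 5/10 x 1.0 = 0.50 SD

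Half-width of a 95% confidence interval for a difference in means, 10 v 10 = t(0.975, 18) x sqrt(1/10 + 1/10) = 2.101 x 0.447 = 0.94 SD.

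Each illustrated shift is smaller than that sampling uncertainty. However, adding comparators reduces the uncertainty and does not reduce a shift caused by a fixed affected share.

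**The case against.** The strongest reply is that the gap is silence, not permission. Aim 3 and the study-procedures paragraph refer to similar characteristics without a closed list, and the items in parentheses elsewhere may be matching variables rather than full eligibility. The team may well intend healthy term comparators. That is fair, and a reader should not infer that the plan sets out to use preterm or ill infants. But a chart reviewer following the text has no instruction to exclude them, and if exclusion is intended, writing it down costs little.

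It is also true that the Technological Advances section is background. It does not describe the hospital's archive, and a scan done for suspected disease can be normal. A reader might infer that the comparison group will be contaminated, or that the bias runs in a known direction. The documents support neither inference: the affected share is unknown, and so are the direction and size of any effect.

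Three further inferences should be resisted:
- **That the absence of covariate adjustment is itself a defect.** With about 10 cases and a descriptive comparison, adjustment is hardly feasible. Eligibility is the practical place to deal with the problem.
- **That comparators could be chosen after their tract values are seen.** The axonal pathway section has comparators identified on head shape first and describes tract construction afterwards. Nothing suggests another order.
- **That the Comparison Sample paragraph's reference to Aim 2 changes the analysis.** The comparison is Aim 3; the label is a clerical slip.

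Finally, this is a pilot, the only planned test is a signed-rank test on paired observations, and the illustrated shifts lie within sampling uncertainty. That limits the weight of the point but does not remove it.

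**Conclusion.** The point holds as an eligibility gap. Comparators are selected on gender, age, race/ethnicity and head shape from existing MRIs, and no section applies the term-birth and health-history criteria that bind the cases. A difference in tracts, or the lack of one, could therefore reflect prematurity or illness among comparators rather than DP.

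Confidence is high that the gap exists. Its effect cannot be sized from the documents; the 0.05 to 0.50 SD range rests wholly on assumed inputs. The point is confined to Aim 3 and to a descriptive comparison. It should be corrected before comparators are selected, but it does not undermine the rest of the study.

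**What to change.** In the two comparison-sample paragraphs and in Brain MRI axonal pathway:

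- Apply Table 1's term-birth and health-history criteria to comparators, leaving out the DP and helmet items.
- Record the clinical indication for each comparator's MRI.
- State that age is matched at scan to the case's pre-helmet MRI, when significant DP is still present.
- Report as a limitation that case scans follow one 3T research protocol (Outcome Measures) while comparator scans are existing records. Tighter eligibility does not remove that difference.
- As a clerical correction, change Aim 2 to Aim 3 in the Comparison Sample paragraph.

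It would be unwise to add a rule rejecting infants whose charts lack cranial symmetry measures. The Head Shape Measures section describes these as routine brace-center measurements, so infants without DP may not have them, and such a rule could remove much of the no-DP group that Aim 3 needs.

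The cost is a few sentences and a stricter chart filter, with no new measurement or patient contact. The downside is fewer eligible comparators; the documents do not show how many would be lost.
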